9.2 SAMPLE SIZE DETERMINATION

Sample Size and Power for primary outcome

In our sample of HIV care facilities with >1,000 clients enrolled overall, we anticipate at least 10% will be eligible adolescents and young adults or about 100-200 AYA per clinic on average. Based on our UG3 data, we assume that 75% will be in care (not LTFU) and viral suppression of 64% (85% suppressed x 75% actively in care). Given a minimum of 20 facilities in the trial (minimum 10 per arm), we estimated the minimum average number of AYA per facility to detect a 15-20% change in retention using EMR data. We assumed 80% power, an $\alpha=0.05$ and coefficient of

Adapted from NIH Behavioral and Social Intervention Clinical Trial Protocol Template v3.0 - 20180827

variation of 0.15. In table 3a below, we can detect a 17% percentage point different (75% to 93%) with an average of 100 AYA per facility and 20 facilities. The same estimates hold for as few as 50 AYA per arm and up to 170 per arm. Detecting less than a 17% percentage point difference would require more facilities per arm or at least 180 AYA per facility.

Secondary outcomes and assumptions:

Viral suppression: An average of 50 AYA VL records per facility and a minimum of 10 facilities per arm would be sufficient to detect a change from 64% to 81%, assuming 80% power, an $\alpha=0.05$ and coefficient of variation of 0.15.

Cohort analyses: Based on UG3 enrollment data in the AYA cohort, we assume that about 50% of the total AYA clinic population to enroll in the cohort and set 50 as the average enrollment target per facility. Separate power and sample size calculations will be performed based on the specific exposure and outcome. When the intervention is the exposure, we will assume to have adequate power to detect at least a 17% percentage point difference in proximate outcomes (e.g. implementation and client outcomes)

Table 3a: Minimum Sample of AYA per Facility for the Primary ITT Analysis of Retention

	Retention % in the intervention arm	n=100 AYA per facility	Facilities per arm	n=50 AYA per facility	Facilities per arm
75%	90%	100	13	50	14
75%	92%	100	11	50	12
75%	93%	100	10	50	10

Table 3b: Summary of sample size estimates by outcome

Outcome	Source	Sample size	
		Intervention	Control
Retention	EMR data	3000	3000
Unsuppressed VL	EMR data	3000	3000
Mediators and secondary outcomes	Adolescent surveys	1500	1500
	Caregiver surveys	450	450
Implementation outcomes	HCW surveys	120	120
	HCW implementation logs	12	0

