2.2. Sample size considerations

2.2.1. Sample size and power for primary outcome

In our sample of HIV care facilities with >1,000 clients enrolled overall, we anticipate at least 10% will be eligible adolescents and young adults (AYA), with about 100-200 AYA per clinic on average. Based on our UG3 data, we assume that 75% will be in care (not LTFU) by the end of 12-month follow-up period. Given a minimum of 24 facilities in the trial (minimum 12 per arm), we estimated the minimum average number of AYA per facility to detect a 14-18% point change in retention using EMR data. Assuming 12 facilities per arm, 80% power, $\alpha=0.05$ and coefficient of variation of 0.10 (Table 2), we can detect a 14%-point difference (75% to 89%) with at least 150 AYA per facility, and a 15%-point difference (75% to 90%) with at least 50 AYA per facility. Assuming coefficient of variation of 0.15, we can detect a 17%-point difference (75% to 92%) with at least 50 AYA per facility (Table 2). Detecting a less than 14%-point difference or if assuming a larger correlation coefficient of individuals within a facility would require more participants per facility or more facilities per arm.

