2.2.2. Secondary outcomes and assumptions

Viral suppression: An average of 50 AYA VL records per facility and a minimum of 12 facilities per arm would be sufficient to detect a change from 64% to 82%, assuming 80% power, an $\alpha=0.05$ and coefficient of variation of 0.10 (Table 2).

Table 1. Sample size calculation of number of facilities per arm for the ITT analysis of retention and viral suppression

AYA per facility	ICC	Estimated proportion in study arm									
		Control	Intervention								
		75%	85%	86%	87%	88%	89%	90%	91%	92%	93%
200	0.10		26	21	18	15	12	11	9	8	7
150			27	22	18	15	12	11	9	8	7
100			27	22	18	15	13	11	9	8	7
50			30	24	20	17	14	12	10	9	8
	0.15	75%	85%	86%	87%	88%	89%	90%	91%	92%	93%
200			39	31	26	21	18	15	13	11	10
150			39	32	26	22	18	16	13	12	10
100			40	32	26	22	19	16	14	12	10
50			42	34	28	23	20	17	14	12	11
		64%	80%	81%	82%	83%	84%	85%	86%	87%	88%
200	0.10		13	11	10	9	8	7	6	6	5
150			13	12	10	9	8	7	7	6	5
100			13	12	10	9	8	7	7	6	5
50			15	13	11	10	9	8	7	7	6
	0.15	64%	80%	81%	82%	83%	84%	85%	86%	87%	88%
200			19	17	15	13	12	10	9	8	8
150			19	17	15	13	12	10	9	8	8
100			19	17	15	13	12	11	10	9	8
50			20	18	16	14	12	11	10	9	8

ICC: intraclass correlation coefficient; sample size estimated by assuming study power of 80%, significance level of 0.05 and coefficient of variation of 0.10

Section 3. Study Data Analysis

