3.5. Analysis of secondary study outcomes

3.5.1. Loss to follow-up:

- Loss to follow-up will be defined as a participant missed a visit and did not return to care within the 12-month study period. The proportion of loss to follow-up during 12-month study interval (window up to 12 months +30 days) will be compared between study arms using Poisson regression with robust errors.
- Time to loss to follow-up will be compared between arms by survival curves, and death or transfers will be censored. The hazard of loss to follow-up will be compared between study arms using Cox proportional hazards regression.

3.5.2. Viral non-suppression:

- Viral non-suppression will be defined as having HIV viral loads (VL) >1,000 copies/mL. Each VL testing result will be classified as VL suppressed vs. unsuppressed. The proportion of viral non-suppression during follow-up will be compared between study arms using mixed-effects Poisson regression with random effects for facility and participant and robust standard errors.

3.5.3. Receiving differentiated care:

- Receiving differentiated care will be defined in two ways. One approach will evaluate the next visit appointment date (scheduled inter-visit interval) – visits scheduled for ≥ 3 months after visit will be considered as differentiated care, in comparison to monthly visits recommended for AYA in current guidelines. The second approach will use the variable ‘fast-track’ at each visit – ‘fast track’ visits are considered as a component of differentiated care. Two analyses will be conducted (one for long scheduled inter-visit interval and one for ‘fast track’), each will be compared between study arms using mixed-effects Poisson regression with random effects for facility and participant and robust standard errors.

3.5.4. Adherence:

- Adherence will be evaluated using the proportion of days of pill dosing over days of inter-visit interval. The level of adherence during the past inter-visit interval will be assessed at each visit. A proportion over 80% as good adherence. The dichotomized adherence will be compared between arms using mixed-effects Poisson regression with random effects for facility and participant and robust standard errors.

Table 5. Analysis of secondary study outcomes

Loss to follow-up				
	Overall	Control	Intervention	Intervention vs. control
	Count (proportion)			^a RR (95% CI) ^b HR (95% CI)
Event Person-year Cumulative incidence Incidence rate (per 100 person-years)				
Viral non-suppression				

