	Overall	Control	Intervention	Intervention vs. control
	Count (proportion) / Median (IQR)			^c RR (95% CI)
Per participant Number of viral load assays				
Over all participants Number of viral load assays Number of non-suppression results (%)				
Differentiated care: long-interval visits scheduled				
	Overall	Control	Intervention	Intervention vs. control
	Count (proportion) / Median (IQR)			^c RR (95% CI)
Per participant Number of scheduled visits				
Over all participants Number of scheduled visits Number of long-duration interval (%)				
Differentiated care: fast-track visits				
	Overall	Control	Intervention	Intervention vs. control

DiSC UH3 Statistical Analysis Plan (SAP)

	Count (proportion) / Median (IQR)			°RR (95% CI)
Per participant Number of visits with non-missing care model				
Over all participants Number of visits with non-missing care model Number of fast-track visits (%)				
Adherence				
	Overall	Control	Intervention	Intervention vs. control
	Count (proportion) / Median (IQR)			°RR (95% CI)
Per participant Number of intervals with good adherence				
Over all participants Number of intervals with good adherence Number of intervals with good adherence (%)				

^a Estimated by Poisson regression with robust errors

^b Estimated by Cox proportional hazards regression

^c Estimated by mixed-effects Poisson regression models with random effects for facility and participant and robust standard errors

*Models adjusted for any factors differing between arm with statistical significance at enrollment

Section 4. Missing data

While we will attempt to follow all participants at 12 months, we anticipate that EMR data and VL data may be incomplete for some participants might be a challenge due to participant loss to follow-up – either due to loss from care, or silent transfer to another facility. Due to the level of missingness we expect, we will not conduct any formal imputation.

Section 5. Safety monitoring

Adverse and severe adverse events, including social harms such as violence or breach of confidentiality, will be monitored as they arise, and unblinded results will be reviewed by the DSMB. The DSMB will make recommendations regarding any imbalances in safety outcomes.

SAE #	PTIDNO	Study arm	SAE description	Onset date	Duration (days / unresolved)	Onset since randomization (days)	Relatedness to study

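### The SAP rules out imputation and adds no missing-data sensitivity analysis, so the secondary viral non-suppression result depends on who was tested, and testing depends on retention

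*SAP*

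**What the plan says.** SAP Section 4 expects that record and VL data may be incomplete for some participants "due to participant loss to follow-up – either due to loss from care, or silent transfer to another facility". It then states: "Due to the level of missingness we expect, we will not conduct any formal imputation". The section names no other method, and neither document pre-specifies weighting, a rule for participants without a result, bounds, or any other missing-data sensitivity analysis. The second viral-suppression analysis in Protocol 8.1 changes the assay threshold only.

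For the viral outcome, SAP 3.5.2 says: "Each VL testing result will be classified as VL suppressed vs. unsuppressed". These results enter a mixed-effects Poisson model with random effects for facility and participant. The denominator in SAP Table 5 is the number of assays, not the number of adolescents enrolled.

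The planning figures have a different basis. SAP 2.2.1 states: "we assume that 75% will be in care (not LTFU) by the end of 12-month follow-up period". Protocol 9.2 derives its planning value as "viral suppression of 64% (85% suppressed x 75% actively in care"). SAP 2.2.2 starts from the same 64%, saying that 50 VL records per facility and 12 facilities per arm "would be sufficient to detect a change from 64% to 82%, assuming 80% power". The heading of its sample-size table describes this as the intention-to-treat sizing.

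**The concern.** If gaps are expected, that is a reason to test how far the result depends on them. It is not a reason to leave the test out.

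The SAP's own explanation for the gaps makes this matter. If adolescents have no VL because they left care, having a VL result is partly a consequence of retention. If DiSC improves retention, the tested groups in the two arms are then selected differently, and the selection is caused by the intervention. A comparison of available assays answers a question about tested adolescents. The 64% base treats the question as one about all adolescents, with those out of care counted as failures.

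Without a sensitivity analysis, a null viral result would be hard to read. It could mean no viral benefit, or a benefit that came through retention and so fell outside the analysed data.

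A related problem affects the secondary loss-to-follow-up (LTFU) outcome. Only participants recorded as transferred or dead are censored (SAP Table 1), so a silent transfer counts as a loss. Protocol 7.3 says study staff will not contact adolescents or caregivers who miss appointments for survey data collection, and no other study tracing step is described.

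**Working it through.** **1. The plan's own figures.**
- Base rate: 0.85 x 0.75 = 0.6375, which rounds to 64%. The 25% not in care contribute no suppression.
- Facilities per arm for 64% v 82%, m = 50, clustering parameter 0.10 used as an ICC, two-sided alpha 0.05 (sidedness assumed), 80% power: (1.96 + 0.8416)² x [0.64 x 0.36 + 0.82 x 0.18] / 0.18² x [1 + 49 x 0.10] / 50 = 10.81, so 11. The SAP table gives 11.

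**2. Inputs for the comparison.**
- Control retention 75% (SAP 2.2.1).
- Intervention retention 89%, from "we can detect a 14%-point difference (75% to 89%) with at least 150 AYA per facility". A second value, 92%, comes from "we can detect a 17%-point difference (75% to 92%) with at least 50 AYA per facility". Both are detectable effects, not forecasts.
- Suppression among the retained 85% (Protocol 9.2), so 15% are unsuppressed. Taking this as equal in both arms is my assumption.
- q, the proportion unsuppressed among the lost. The documents give no estimate. The planning product implies q = 100%, and other values are assumed.
- Limiting case: every lost adolescent has no VL result, and every retained one has a result.

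**3. Available-case comparison.** Only the retained contribute: 15% v 15% unsuppressed, risk ratio 1.00.

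**4. All-adolescent comparison.** Control = 0.75 x 0.15 + 0.25q. Intervention = 0.89 x 0.15 + 0.11q.

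| q (unsuppressed among the lost) | Control | Intervention | Risk ratio |
|---|---|---|---|
| 100% | 0.3625 | 0.2435 | 0.67 |
| 70% | 0.2875 | 0.2105 | 0.73 |
| 50% | 0.2375 | 0.1885 | 0.79 |
| 30% | 0.1875 | 0.1665 | 0.89 |
| 15% (as among the tested) | 0.1500 | 0.1500 | 1.00 |

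The first row corresponds to suppression of 63.8% v 75.7%, a difference of 11.9 points. With 92% retention and q = 100%, the intervention value is 0.92 x 0.15 + 0.08 = 0.218, and the risk ratio is 0.218 / 0.3625 = 0.60.

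**5. The equal-suppression assumption.** Suppose instead that the extra 14% retained are only 50% suppressed (assumed) and none of the lost are. Overall intervention suppression is 0.6375 + 0.14 x 0.50 = 0.7075, so the all-adolescent risk ratio is 0.2925 / 0.3625 = 0.81. Among the tested, suppression is 0.7075 / 0.89 = 0.795 v 0.85, a risk ratio of 1.37. The available-case figure therefore need not be 1.00, and it can point the other way.

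**The case against.** Several points on the other side stand.

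- **The analysis is available-case, not complete-case.** All results from enrolment to 12 months are used, so an adolescent tested before leaving care still contributes. VL data come from the national (NASCOP) laboratory database and paper records, which may recover some silent transfers. Being lost and having no VL are different things: Protocol 8.1 describes routine testing 6 months after ART initiation and then annually. The limiting case therefore overstates the gap.
- **The SAP does not say missingness will be high.** A reader might infer this from the cited reason and the assumed 25% loss. The text says only that data may be incomplete for some participants.
- **Among those tested, 1.00 is the correct answer.** In the table above, the whole all-adolescent difference comes from retention, which the trial analyses directly through missed visits and LTFU.
- **Power would be limited anyway.** By the SAP table's variance method, with 12 facilities per arm, 150 adolescents each and ICC 0.10, fully observed data would give about 7%, 15%, 27% and 50% power at q = 30%, 50%, 70% and 100%. The sensitivity analyses help interpretation. They will not rescue a significance test.
- **Differential testing will be partly visible.** SAP Table 5 reports assays per participant by arm. A median and IQR do not, however, show how many enrolled adolescents had no result.

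A reader might also infer that the primary outcome is compromised. The documents do not support that. Not being seen within 30 days of a scheduled visit is itself the event, so most loss is counted as outcome; only appointments with censored or missing status are excluded (SAP Table 4).

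None of this supplies the missing sensitivity analysis, or makes expected missingness a reason to omit one.

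**Conclusion.** The point holds for secondary outcomes, chiefly viral non-suppression. The SAP gives expected missingness as its reason for not imputing, puts nothing in its place, and analyses available assays although the trial was sized on a figure that counts the lost as not suppressed.

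In the limiting case at 89% retention, an available-case risk ratio of 1.00 can sit beside an all-adolescent ratio anywhere from 0.67 to 1.00, depending on suppression among the lost. That range rests on 75% v 89% retention, 85% suppression among the retained in both arms, and no VL result for anyone lost. Earlier tests and laboratory records would narrow it.

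It would be wrong to read this as a prediction that the trial will report 1.00, or as evidence that 0.67 is the true effect. The documents support neither. What they show is that the plan has no means of telling these situations apart. This should be changed because the remedy is cheap; it does not invalidate the trial.

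**What to change.** Keep the planned analysis and delete the sentence that gives expected missingness as the reason for not imputing. Report by arm how many enrolled adolescents have at least one VL in the window, and how many have none, split by whether they were still in care. Pre-specify three sensitivity analyses:

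1. **Per-participant viral outcome in all enrolled adolescents.** Those with no VL in the window and not in care count as unsuppressed. Those in care but untested are handled separately, because counting them as failures would confuse testing with suppression. Testing may differ by arm, since the sample steps in Protocol 6.1.1 include accelerated repeat testing.
2. **Multilevel multiple imputation or inverse-probability weighting**, using arm, clinic, age, sex, last VL and visit history, with a delta or tipping-point range for those lost. Without that range, the method assumes the lost resemble comparable adolescents who were tested, which is the assumption in doubt.
3. **Tipping-point analysis for the secondary LTFU outcome**, varying the share of unexplained losses that are silent transfers from 0% to 100%, separately by arm.

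The cost is extra analysis work only. Design, data collection and the primary analysis are unchanged.
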